The occurrence and intensity of anxiety or panic responses can be reduced through providing participants with information on potential drug effects, supervision and monitoring of participants for the duration of drug effects, and using ascending dose designs. The goal in this study is to treat participants undergoing anxiety or panic reactions first by verbal and psychological interventions, and using anxiolytic medication only after verbal and psychological interventions have failed, and if participants are endangering themselves or others.

In case of insomnia the investigator may prescribe a benzodiazepine or zolpidem as a “rescue medication” for the day or night after an experimental session. Residual symptoms will be addressed during the frequent follow-up psychotherapy visits with the investigators.

Reckless or self-injurious behavior

People who have taken serotonergic psychedelics, as LSD, in uncontrolled settings may engage in reckless behavior, such as driving while intoxicated. The risk of reckless behavior occurring during controlled studies can be prevented or greatly reduced through continued supervision by the researchers and requiring all participants to remain at the practice for 23 hours after each drug administration.

Psychosis, suicidal thoughts or impulses

As is true of the pharmacologically similar compound LSD, psilocybin use is associated with transient and sometimes prolonged psychotic states in users (Benjamin 1979; Halpern and Pope 1999). Researchers who reviewed case series and reports that associated LSD or serotonergic psychedelics more generally with subsequent occurrence of psychosis note that diagnosis of psychosis is made only after drug use, and not prior to it (Strassman 1984). After examining the literature, Strassman concluded that LSD might trigger psychotic episodes in people already vulnerable to psychosis but that it did not directly cause psychosis in people not susceptible to it. Two large studies surveyed clinicians or researchers who had conducted LSD research or LSD-assisted psychotherapy (Cohen 1960; Malleson 1971) and found the prevalence of psychiatric symptoms after participation to be very low. None of the participants in recent psilocybin studies experienced psychotic states, though some participants exhibited transient paranoia or some loss of insight into the situation during the course of psilocybin effects (Gouzoulis-Mayfrank et al. 1999b; Griffiths et al. 2006; Vollenweider et al. 1997). These findings suggest that while psilocybin can provoke psychosis or other psychiatric symptoms in a very small percentage of people, it does not do so often, and that receiving a psychedelic drug as part of a research study is extremely unlikely to trigger transient or persistent psychosis. The occurrence of transient or persistent psychosis can be prevented or further reduced by screening subjects on the basis of past and current mental health. Subjects with a personal or family history in first-degree relatives of psychosis (bipolar disorder or schizophrenia), or suicide attempts will be excluded from this study.

If a participant should become psychotic or suicidal for a time exceeding the duration of drug effects and the investigators are unable to ameliorate these symptoms, arrangements will be made for him or her to be admitted to the nearest inpatient psychiatric facility at the clinic.

Chronic neuropsychological effects

Earlier studies found changes in personality or neuropsychological function after frequent chronic LSD use. However, a review of these studies concluded that they all shared a number of methodological flaws (Halpern and Pope 1999) that included retrospective study design, failure to account for effects of other drugs, possible pre-existing morbidity, and the association of LSD with subcultures that valued specific personality types. In their review and analysis, Halpern and Pope concluded that long-term changes in personality or psychological function, if they existed at all, were liable to be subtle or not clinically significant (Halpern and Pope 1999). It is notable that two months after psilocybin administration, investigation in psilocybin-naïve individuals, investigators found that friends or relatives of the study participants stated that after participants received psilocybin, they underwent positive changes in their attitudes and behavior (Griffiths et al. 2006).

Some people who have used serotonergic psychedelics, such as LSD or psilocybin, experience persistent and distressing alterations in mostly visual perception that last from weeks to years after use. This condition is now diagnosed as hallucinogen persistent perception disorder (HPPD), and is not referred to by the term “flashbacks,” which better

describes an experience more akin to traumatic recall of an intensely upsetting experience, as a “bad trip.” By contrast, HPPD involves changes in visual perception rather than a re-experiencing of feelings or memories first experienced while under the influence of a psychedelic. There is a paucity of data concerning the prevalence of HPPD due to psilocybin use.

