10. Are able to communicate in English.

Exclusion Criteria

Prospective participants with the following conditions will be excluded:

1. Meet DSM-IV criteria for bipolar disorder, schizophrenia, or other psychotic disorders.

2. Meet DSM-IV criteria for abuse of or dependence on any substance (other than caffeine or nicotine) in the past 60 days.
3. Have first-degree relatives (as parent or full sibling) with past or present psychiatric disorders, including schizophrenia, bipolar affective disorder and other psychoses, but excluding mood disorders.
4. Cannot have a current diagnosis of anxiety disorder that predates diagnosis with melanoma.
5. Have used psilocybin or psilocybin-containing mushrooms within the past year.
6. Require concomitant treatment with anti-psychotic medications, prescribed for the management of either psychiatric symptoms or nausea. The restriction on 5HT_{2C}/5HT₃ antagonists is applicable for 24 hours before and including the day of the study.
7. Are cachectic as indicated by loss of 10% or greater of their total weight.
8. Have been diagnosed with primary or metastatic cancer of the CNS confirmed by MRI, within 6 weeks of participation in the study.
9. Have uncontrolled hypertension.
10. Have baseline laboratory values indicative of severely compromised hepatic function, indicated by unacceptable levels of alkaline phosphatase (ALP) above 750 U/L. Participants must also have laboratory blood screening indicating ALP below 750 U/L immediately prior to administration of psilocybin.
11. Are women who are pregnant or nursing, or of child bearing potential and are not practicing an effective means of birth control.
12. Are reasonably judged to present a serious suicide or homicide risk or who are likely to require psychiatric hospitalization during the course of the study.
13. Are unable to fully understand the potential risks and benefits of the study and give informed consent.

Planned Duration of the Study

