After giving written consent, participants will be screened for presence of anxiety and for the presence of any psychiatric conditions that preclude study participation, such as psychosis. The principal investigator will conduct the screening evaluation in his office. The Structured Diagnostic Clinical Interview (SCID) will be used for diagnosing anxiety and detecting any conditions that preclude study participation, and the Mini Mental State Evaluation (MMSE) will be used to determine mental state and competency to take part in the study. Only participants with MMSE scores of 27 or higher will be eligible for study participation. The Hospital Anxiety and Depression Scale (HADS) will be used to quantify anxiety. Only people who are diagnosed with anxiety via SCID or who have a HADS Anxiety score of eight (8) or higher will be eligible for study participation. Once it is determined that participants meet study eligibility criteria, participants will complete or undergo additional assessments of anxiety and depression, quality of life and functional status, described above. The primary caregivers will complete the HADS. The investigators will also provide participants with daily pain and medication diaries and instructions on how to complete them. Participants will begin completing daily pain and medication diaries starting after baseline analysis.

Randomized blinded Study phase

Randomization

Upon enrollment into the study, participants will be assigned to one of two conditions, active placebo (4 mg psilocybin) or full experimental intervention (25 mg psilocybin). Active placebo in this study is a low dose of the investigational drug that will not produce the unique effects of psilocybin. Participants have a 66% chance of assignment to the full experimental intervention, with six of nine participants will be assigned to receive the full experimental intervention and three will be assigned to receive active placebo. The internal review committee coordinator at the study site will generate and maintain the randomization code and procedure. Condition assignment will be maintained from study enrollment up through the course of the study, as there is no crossover design. If there is an adverse event or other emergency requiring knowledge of participant's condition assignment, as when pharmacological intervention is necessary, the blind may be broken for an individual participant.

Introductory Psychotherapy Session (Visits #4 and #4.5)

Psychotherapy

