Participants must be able to complete self-report measures and understand and answer items in clinician-administered measures. The investigators will perform the MMSE to assess mental status and review medical records for indicators of subsequent metastasis or other CNS disease since the end of the randomized or open-label phase. Only participants with MMSE scores of 27 or higher and without any signs of serious CNS disease will undergo assessments at this time. Participants will complete the HADS, STAI, FACIT-Sp, EORTC-QLQ-C15 and SELF, and the investigators will administer the HAM-A and HAM-D and a pain level measurement for the day of the two-month follow-up. The investigator will assess participants for symptoms of HPPD by asking about cardinal symptoms of perceptual disturbances and distress at their occurrence.

Visit by Visit Description

Participants who consent to take part in the study will undergo the following sequence of events:

The randomized, blinded study phase:

- **Psychiatric Evaluation and Baseline (Visit 3):** A two-hour long psychiatric evaluation. The principal investigator will diagnose psychiatric disorders via SCID. Mental status will be assessed with MMSE. Participants will also complete measures of anxiety (HADS anxiety, STAI), depression (HADS depression), spirituality (FACIT-SP) and quality of life (EORTC-QLQ-C15). The investigators will also administer observer-scored measures of anxiety (HAM-A), depression (HAM-D), and ability to perform everyday life functions (KPRS). If a participant meets study eligibility criteria after psychiatric evaluation, he or she will be scheduled for an introductory psychotherapy session.

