Rescue medication will only be used if an individual is endangering him or herself or others, or at the discretion of the investigator. The use of prescribed rescue medicines during an experimental session is contraindicated because it can interrupt the therapeutic process, although it would not be expected to cause any physical harm to the subject. The goal of the process is to confront fears and to experience them fully as a means of coping with them, and participants are likely to feel anxious during the course of the experimental session.

The investigators will query subjects about suicidal ideation or intent during screening, and prior to each psilocybin session. Participants who evidence suicidal ideation or intent will be withdrawn from the study and referred to appropriate psychiatric care.

If a psychiatric hospitalization is necessary, participants will be admitted to the study site, which is on the same campus as the clinic. The hospital will be informed in advance about the study.

Medical Emergencies

Basic emergency equipment is available in the cancer center. The principal investigator's office is located in the study site, on the same grounds as the clinic. The hospital will be informed in advance about the nature of this study.

The investigators will assess blood pressure at least five times during the experimental session; immediately prior to drug administration, and hourly for the next three hours. The investigators will make more frequent measures if in their judgment these are warranted. The clinic will have the appropriate medications and equipment to treat hypertension or cardiac problems if they should arise. The slight elevations in blood pressure or heart rate after psilocybin are not expected to cause any problems or cause any adverse events requiring medical intervention.

An adverse event (AE) is defined as any untoward medical occurrence in a patient or clinical investigation subject administered a pharmaceutical product at any dose that does not necessarily have to have a causal relationship with this treatment. An AE can, therefore, be any unfavorable and unintended sign (including an abnormal laboratory finding, for example), symptom, or disease temporally associated with the use of an investigational product, whether or not considered related to the investigational product. This definition includes concurrent illnesses or injuries and exacerbation of pre-existing conditions.

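### The risk section excludes people with suicide attempts, but no numbered eligibility criterion or planned suicidality query covers attempt history

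*Protocol*

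**What the plan says.** Under Risk of the Experimental Drug, in the subsection on psychosis and suicidal thoughts, the protocol explains that screening on past and current mental health lowers the risk of psychosis. It then says that subjects with a personal or first-degree family history of psychosis "or suicide attempts will be excluded from this study". The statement has no qualifier.

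The Exclusion Criteria section opens with "Prospective participants with the following conditions will be excluded" and lists 13 items. Three are relevant:

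- Item 1: "Meet DSM-IV criteria for bipolar disorder, schizophrenia, or other psychotic disorders".
- Item 3, on first-degree relatives: "with past or present psychiatric disorders, including schizophrenia, bipolar affective disorder and other psychoses, but excluding mood disorders".
- Item 12: "Are reasonably judged to present a serious suicide or homicide risk or who are likely to require psychiatric hospitalization".

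Under Acute Psychological Distress: "The investigators will query subjects about suicidal ideation or intent during screening, and prior to each psilocybin session". People who show ideation or intent are withdrawn and referred.

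Under Screening and Baseline evaluation: "The Structured Diagnostic Clinical Interview (SCID) will be used for diagnosing anxiety and detecting any conditions that preclude study participation". The Visit by Visit Description gives Visit 3 as "A two-hour long psychiatric evaluation. The principal investigator will diagnose psychiatric disorders via SCID".

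**The concern.** The risk section promises an exclusion based on history. The eligibility list, which site staff work from, contains no such exclusion. A person who attempted suicide years ago and now shows no ideation, intent or judged serious risk would meet the list and still be someone the protocol says is excluded.

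The gap can be reached in practice. Past major depression is not an exclusion, since item 1 covers only bipolar and psychotic disorders, and inclusion item 8 asks participants to stay off antidepressants during the study.

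Safety is part of the primary objective. The Data Analysis section treats a single serious adverse event possibly or probably related to the drug as an indicator that the treatment is not safe in this population. With so few participants, one enrolment that the protocol itself rules out could drive the safety conclusion.

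**Working it through.** No statistical calculation applies, and the protocol states no figure to reproduce. The check sets each part of the risk-section sentence against the places where eligibility is applied.

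**Step 1. Map the sentence to the numbered criteria.**

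| Part of the risk-section exclusion | Numbered criterion |
|---|---|
| Personal history of psychosis | Exclusion 1 (loosely: the item speaks of meeting diagnostic criteria and does not spell out past illness) |
| Psychosis in a first-degree relative | Exclusion 3 |
| Suicide attempts | None: 0 of 13 exclusion items, 0 of 10 inclusion items, so 0 of 13 + 10 = 23 |

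**Step 2. Test the nearest item.** Exclusion 12 requires that the investigator judge a serious suicide or homicide risk, or a likely psychiatric hospitalization during the study. A past attempt may inform that judgement, but it does not by itself meet the item.

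**Step 3. Test the planned queries.** In the randomized phase there are three: screening, Visit 5 and Visit 8. The open-label sessions at Visits 13 and 16 make 3 + 2 = 5, or 6 if the open-label re-screening also counts. All concern ideation or intent, as does the withdrawal rule. None asks about past attempts.

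**Step 4. Test the sample case report forms (Appendix B).** The enrollment decision asks the principal investigator to review source data and the inclusion and exclusion criteria. The Visit 5 pre-dose check asks again whether those criteria are met. The baseline forms have no field for past attempts. A suicide-risk code appears at Visits 4 to 6, after enrollment at Visit 3, and it records risk, not history.

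**Step 5. Test the family scope.** The sentence can be read as the subject's own attempts, or as attempts in the subject or a first-degree relative. Item 3 does not settle this: it concerns relatives' psychiatric disorders, sets mood disorders aside and does not mention attempts. Neither reading has a matching criterion.

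**Size.** The number of affected people cannot be computed, because the protocol gives no prevalence of past attempts. Among nine completers, one person is 1/9 = 11%.

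**A separate wording slip.** Medical Emergencies says blood pressure is taken at least five times per session, then lists one pre-dose and three hourly readings: 1 + 3 = 4. The session descriptions for Visits 5, 8 and 13 also give four. This has no bearing on the eligibility point.

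**The case against.** The strongest reply is that the protocol binds as a whole. The risk section is protocol text, the eligibility list is merely silent, and nothing in it admits a person with a past attempt. On that view this is a missing cross-reference, and an investigator who follows the whole document would exclude. It can be added that the structured interview covers lifetime as well as current disorders and is meant to detect precluding conditions, that item 12 lets the investigator weigh a past attempt, and that the forms code suicide risk before the first dose.

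Much of this is fair. It is an internal inconsistency and not a flaw in the trial's design, and the safeguards narrow the gap. They do not close it. The interview may bring an attempt to light, but no numbered item says to exclude on it. Item 12 and the risk code rest on judgement or current state. The enrollment and pre-dose checks run off the criteria, so a condition stated only in the risk section is easily missed.

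It can also be said that the risk section and the list are loosely aligned in general. The subsection on chronic neuropsychological effects speaks of excluding people who report persisting perceptual disturbance after earlier hallucinogen use, and that too is missing from the list. This is correct, and it is a reason to reconcile the two sections fully.

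**Conclusion.** The concern holds. The protocol states an exclusion for suicide attempts that appears in 0 of its 23 numbered criteria and in none of its planned suicidality queries. Following the list alone could lead to dosing someone the protocol says is excluded. This should be corrected.

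The conclusion assumes only that sites apply eligibility from the numbered criteria, as the sample enrollment and pre-dose forms direct. It makes no claim about how often such a person would present, and it has no effect on the sample size, power or primary analysis. The existing evaluation, item 12 and the ideation and intent queries reduce the practical risk but do not replace an exclusion based on history.

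**What to change.** Add a numbered exclusion 14: *Have a history of suicide attempt.* State in the same item whether a first-degree relative's attempt also excludes. Ask about it at the Visit 3 psychiatric evaluation, before enrollment, and add a field for the answer to the baseline form. Reword the risk-section sentence to match.

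If the sponsor does not intend the exclusion, delete the reference to suicide attempts from the risk section and give the reason. Adding the criterion is preferable because it keeps the stated protection.

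In the same amendment, correct the blood pressure count under Medical Emergencies from five to four, or add a fixed fifth reading there and in the session descriptions. Check the other exclusions stated in the risk section against the list, including the one on persisting perceptual disturbance.

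The cost is one criterion, one question within a two-hour evaluation already planned, one form field and a few wording edits. The downside is a slightly smaller eligible pool.

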There is scant literature on potential drug-drug interactions between psilocybin and other medications or psychoactives, and a review addressing the pharmacology of psilocybin fails to mention any interactions of note (Passie et al. 2002). Research studies in humans demonstrated that drugs that antagonize the 5HT_{2A} receptor may attenuate or eliminate most of the subjective effects of psilocybin, very likely including therapeutic effects (Carter et al. 2007; Vollenweider et al. 1998) and that D₂ receptor antagonists, as haloperidol, attenuate effects on positive mood and increased anxiety (Vollenweider et al. 1998). Surveys of recreational users of serotonergic psychedelics, including psilocybin, suggests that selective serotonin uptake inhibitors (SSRIs) may at first enhance psychedelic effects, but that chronic SSRI treatment attenuates drug effects, and that treatment with MAOIs also attenuates the effects of LSD in humans (Bonson et al. 1996).

By contrast, a chronic course of tricyclic antidepressants may amplify the psychedelic effects of serotonergic psychedelics, likely including psilocybin (Bonson and Murphy 1996).

Early research in rats found that opioid agonists attenuated LSD-associated behavior in rats, such as changes in body posture and disruption of operant conditioning for food reward, while opioid antagonists enhanced these behaviors (Domino 1986; Ruffing and Domino 1981). As noted in “Drug Description and Dose” above, [name], the principal investigator conducting the study of psilocybin-assisted psychotherapy in people with advanced stage cancer, reported that opiates attenuated the effects of psilocybin, but otherwise produced no adverse drug-drug interactions (Grob 2007). This pilot study of psilocybin-assisted psychotherapy may contribute to knowledge of the safety of psilocybin in a medical setting, but based on the existing literature, we are taking appropriate cautions.

Abuse Liability

Currently psilocybin has been placed in the most restrictive schedule of drugs in the US (Schedule 1), defined as having no medical use and having high abuse liability. Despite this designation, examining use patterns in humans and self-administration and conditioned aversion in nonhuman primates suggest that psilocybin possesses little abuse potential. See the section on drug dependence and abuse potential in “Additional Information” for research findings on abuse potential and self-administration of psilocybin.

Risks of Active Placebo dose of Psilocybin

The 4 mg dose of psilocybin used in this study is expected to produce some but not most of the effects of the full 25 mg dose. These include slight changes in perception, cognition or mood, such as slight increases in positive or negative mood or lights or colors seeming brighter. This dose is not expected to produce potentially therapeutic effects, such as amplifying or generating intense mystical or transformative experiences. When combined with psychotherapy, the active placebo dose is not expected to reduce anxiety to the same degree as the experimental intervention dose. It is necessary to employ an active placebo so as to have a controlled study and to maintain the blind concerning condition assignment. Participants who learn they received active placebo will have the opportunity to consent to undergo an open-label study continuation immediately upon learning that they received active placebo.

Alternative Treatments and Procedures

The primary alternative to study participation is not to take part in the study. There are a number of recognized treatments for anxiety arising from diagnosis with a potentially fatal illness such as stage IV melanoma. Treatment often includes both psychotherapy and medication. Most commonly recommended psychotherapeutic treatments include stress management, cognitive therapy, exposure therapy, and psychodynamic psychotherapy. Medications that may ameliorate symptoms of anxiety include

antidepressants (SSRI or tricyclic), benzodiazepines, and mood stabilizers. Participation in this study is entirely voluntary, and refusing to take part in this study will not affect the care the participant is already receiving for anxiety arising from advanced stage illness. Nor will declining to participate affect any care he or she is receiving for stage IV melanoma. Participants will not be penalized for withdrawing from the study.

Confidentiality

Every effort will be made to strictly safeguard the confidentiality of all participants. Despite this, privacy cannot be guaranteed. Prior to and upon entry into the study, participants will be assigned a unique subject number (see “Subject numbering” above). Data collected from each participant will be identified only by the participant’s initials and subject number on source documents. All communication concerning the participants, including communications relating to statistical data gathering from the tests and measurements, will use subject number only and not the participant’s name. All data, measures, records and recordings, and information linking subject numbers to the names of participants will remain at the office of the principal investigator within a locked file cabinet. Access to measures will be limited to regulatory agencies and researchers assessing the participant for changes in symptoms and individuals analyzing data. Researchers with access to data will not be provided with any information that would identify participants by name or by other means.

Costs to Participants

There will be no costs to participants for any of the study procedures, including receiving the study drug or remaining at the practice site for the duration of the experimental session and staying overnight after each drug administration day. The sponsor, MAPS, will pay for all study drugs and study procedures. Participants will not be paid for their participation in this study.

Risk/Benefits Analysis

Anxiety arising from diagnosis with Stage IV melanoma places an additional burden on people who already face a short estimated life expectancy and who must also deal with the sometimes debilitating side effects of cancer treatments. Coping with anxiety in addition to the strains of contending with an aggressive cancer reduces quality of life and may interfere with maintaining relationships and completing life goals. Existing treatments for anxiety may not help everyone, and some treatments, such as benzodiazepines, come with unwanted side effects such as sedation, memory impairment and physical dependence. Given that people with an aggressive cancer may already be taking several different medications to treat their cancer, pain arising from the cancer, and nausea arising from cancer treatments, people with stage IV melanoma may not wish to take additional medications for anxiety.

Psilocybin, like other psychedelic compounds, can powerfully alter affect (mood, feelings), cognition and perception. Psilocybin can produce life-changing experiences that reduce anxiety in the face of imminent death, but it can also produce severe anxiety, panic reactions and transient psychotic states in some individuals. While intense, these experiences are for the most part transient and treatable, and relatively rare. Psilocybin

likely produces intensely beautiful or moving and transformative experiences through the same processes as produce anxiety and panic. Psilocybin has minimal toxicity, and no one has reported a verifiable fatality from psilocybin. The substance has been used in psychotherapy during the 1960s, with psychiatrists and researchers administering psilocybin to thousands of people. Psychotherapists stopped conducting psilocybin-assisted therapy when the drug was made illegal, and not because of any untoward events that occurred during therapy.

Currently, several studies that were just completed in the US and Europe (Griffiths et al. 2006; Hasler et al. 2004; Moreno et al. 2006) have reported safely administering psilocybin in healthy people and in people with OCD, and an ongoing study continues to administer psilocybin to people with advanced stage cancer (Grob 2005). Careful screening, offering a supportive environment and teaching means of dealing with intense anxiety will reduce the likelihood and severity of the adverse effects of psilocybin. Despite psilocybin's capacity to generate profound alterations in consciousness, it possesses little to no physiological risks, has low abuse liability, and also has the capacity to attenuate anxiety and facilitate positive changes in attitude and behavior.

A third of the study participants will receive "active placebo" doses of psilocybin, with "active placebo" connoting a dose that is not expected to produce therapeutic effects. However, these participants will still undergo up to four non-drug psychotherapy sessions plus psychotherapy conducted during each experimental session with active placebo. Once the blind has been broken for each individual, participants who received active placebo may immediately enroll in an open-label study continuation wherein they receive a fully active dose of psilocybin as soon as such a session can be scheduled. An active placebo group is required in order to properly assess the efficacy of study drugs, and an active placebo is required when dealing with strong psychoactives such as psilocybin. Because serotonergic psychedelics produce a unique array of effects that are hard to replicate through other means, the active placebo in this study is a low dose of psilocybin expected to produce some but not all of the drug's cardinal effects.

After taking into consideration the costs and benefits associated with the current study versus alternative treatments available for people with anxiety relating to their cancer diagnosis, we conclude that the benefits of conducting the proposed study outweigh the risks, as the risks are minimal and this innovative treatment, if found to be efficacious, has the potential to help many people experiencing intense anxiety in addition to an aggressive cancer.

Patient's Rights/Insurance

All patients will receive the Informed Consent before enrolling in the study. In the first investigational interview, the investigators will ensure that participants understood the study design as described in consent documents. The investigators will let participants know that they can stop their participation at any point of the study without negative consequences for them and without giving any reason for their decision.

The sponsor will pay for all study-related assessments and therapy. The sponsor will be responsible for payment in treating study-related injuries. Participants will pay for any care not related to the study.

Record Retention

Investigators must retain all study records required by MAPS and by the applicable regulations in a secure and safe facility. The investigator must consult a MAPS representative before disposal of any study records. "Essential documents" are defined as documents that individually and collectively permit evaluation of the conduct of a trial and the quality of the data produced. It is the responsibility of the sponsor to inform the investigator/institution as to when these documents no longer need to be retained.

Chemistry, Manufacturing and Control Information

The study drug is psilocybin, 4-phosphoryloxy-N,N-dimethyltryptamine), a tryptamine first isolated from psilocybe mushrooms by Albert Hofmann, the discoverer of LSD, in 1957, and later synthesized by him in 1958 (Passie 2005). Psilocybin will be administered orally in the form of opaque capsules. The supplier of psilocybin is Organix. The psilocybin is from the same batch manufactured for [name] for his study of psilocybin in people with obsessive-compulsive disorder. This manufacturer has supplied psilocybin to [name] for the ongoing study of psilocybin-assisted psychotherapy in people with advanced stage cancer. A Certificate of Analysis issued by the manufacturer to the sponsor on November 14, 2007 states that the sample is 100% pure.

Psilocybin will be compounded by the pharmacy at the University of Arizona. The pharmacist will pre-randomize all capsules. Full (25 mg) and placebo (4 mg) doses of psilocybin will be placed in opaque capsules of identical size. An inert substance, such as lactose, will be added to placebo capsules so that they weigh the same as full dose capsules. All psilocybin will be handled and stored in accordance with federal and state regulations concerning Schedule 1 substances.

MAPS claims categorical exclusion from the requirement to submit an environmental assessment (21 CFR 25.15[a]). MAPS claims categorical exclusion (under 21 CFR 25.31[e]) for the study under this IND. To its knowledge, no extraordinary circumstances exist.

Pharmacokinetics and Pharmacodynamics

Primary Pharmacology

Psilocybin (4-phosphoryloxy-N,N-dimethyltryptamine, also referred to as 3-[2-(Dimethylamino)ethyl]-1H-indol-4-yl dihydrogen phosphate ester), one of the chief psychoactive compounds found in mushrooms in the genus psilocybe (as psilocybe cubensis, p. semilanceata, p. mexicana). Its chemical formula is $C_{12}H_{17}N_2O_4P$.

It is likely that psilocybin and LSD both alter consciousness through similar mechanisms of action (Aghajanian and Marek 1999; Nichols 2004), acting as 5HT_{2A} agonists. Psilocybin acts upon several serotonin receptors, including 5HT_{1A}, 5HT_{2A} and 5HT_{2C} receptors (McKenna et al. 1990; Passie et al. 2002). Psilocybin does not act directly on dopamine receptors, and there is no current information on its actions on newly discovered serotonin receptors, as 5HT_{5A} or 5HT₇. Large doses of psilocybin (25 mg/kg) increased the presence of a norepinephrine metabolite (Stolk et al. 1974), but it is unclear if this action occurs at typical human doses.

Primary Pharmacodynamics

Drug Activity Related to Proposed Action

Research conducted during the 1950s and 1960s found that psilocybin, like LSD, can be used in combination with psychotherapy (Passie 2005; see for example (Fontana 1961; Leary et al. 1963). Therapists used some of the subjective effects of these serotonergic hallucinogens to stimulate or uncover unconscious feelings or memories and to facilitate breaks with routine or habitual behavior. In the psychotherapy context, potentially therapeutic effects of psilocybin include changes in ego boundary, stimulating unusual thoughts and views of the self and the world, and mood lability. From a traditional psychodynamic viewpoint, a less rigid or more expanded ego boundary and viewing the self or the world in a new perspective can offer a chance for insight, and profound changes in mood and can facilitate confrontation with these emotions. Furthermore, psychotherapy utilizing serotonergic hallucinogens consistently contained spiritual elements which in and of themselves seemed to have profound, positive effects on patients (Griffiths et al. 2006; Pahnke 1963). All three combined may help produce mystical or transformative experiences. These effects of psilocybin may help reduce anxiety when experienced in a safe and supportive environment. However, none of these early studies sought to examine the pharmacological bases of these effects, and to date, there are still no studies that tie a specific putative therapeutic effect of psilocybin with a specific pharmacological action. All serotonergic hallucinogens appear to share activity at 5HT_{2A} receptors, suggesting that these receptors are necessary, but not sufficient, for producing alterations in affect, cognition and perception (Nichols 2004). Psilocybin exhibits an affinity for 5HT_{2A} receptors (McKenna et al. 1990) and it has a stronger affinity for human than rat 5HT_{2A} receptors (Gallaher et al. 1993). Administration of the 5HT_{2A}/5HT_{2C} antagonist ketanserin attenuated subjective effects of psilocybin (Vollenweider et al. 1998) and reduced psilocybin effects on visual perception (Carter et al. 2005a). It is possible that psilocybin alters consciousness through compound-specific alterations in secondary messenger signaling upon activating 5HT_{2A} receptors (“allosteric receptor trafficking”), as both psilocybin and LSD stimulate the arachidonic acid pathway when activating rat 5HT_{2A} receptors (Kurrasch-Orbaugh et al. 2003). While a study chiefly comparing LSD with the non-hallucinogenic compound lisuride in mice suggests that serotonergic hallucinogens produce at least some of their subjective effects through selective stimulation of secondary messengers, researchers have not examined psilocybin in similar studies. Finally, it is possible that some of the potentially therapeutic effects of psilocybin are the result of changes in gene expression stimulated by 5HT_{2A} receptor activation (Gonzalez-Maeso et al. 2003; Nichols and Sanders-Bush 2002). It is not clear
